8.3.2 Proportion and Confidence Interval for Proportions

The proportion is calculated by the following formula unless otherwise instructed:

$$\text{Proportion(%) = } \frac{\text{Applicable subjects}}{\text{Subjects in the analysis population}} \times 100$$

$$\text{AE(%) = } \frac{\text{The number of subjects with AEs}}{\text{Subjects in the analysis population}} \times 100$$

For two-sided 95% CI for proportion, exact test will be used.

Regarding sample code, refer to Appendix 1.

8.3.3 Change from Baseline

Change from baseline at each time point is defined by the following formula:

$$\text{Change from baseline} = \frac{\text{Value at each time point}}{\text{Baseline value}} - 1$$

8.3.4 Study Day

Study day is calculated as follows:

Study day = assessment/event date – first dose date (if assessment/event date < first dose date).

Study day = assessment/event date – first dose date + 1 (if the assessment /event date \geq first dose date)

8.3.5 Statistical Method

No statistical testing will be conducted unless otherwise noted.

8.4 Rounding Digits

8.4.1 Displaying of Descriptive Statistics

- 1) Parameters except for avatrombopag concentration
 - Mean, median, first quartile, third quartile and 95% CI for mean will be displayed in one digit lower than the display digit.
 - Standard deviation will be displayed in two digits lower than the display digit.
 - Minimum and maximum will be displayed in display digit.
- 2) Avatrombopag concentration

Minimum, maximum, mean, standard deviation, median, geometric mean and 95% CI of geometric mean will be rounded and then displayed as 3 significant digits.

The example of rounding and displaying as 3 significant digits:

| Value | Displayed as 3 significant digits |
|----------|-----------------------------------|
| 1234.5 | → 1230 |
| 1.2345 | → 1.23 |
| 243467 | → 243000 |
| 243667 | → 244000 |
| 0.057226 | → 0.0572 |
| 0.057276 | → 0.0573 |

8.4.2 Proportions (%), CV (%), Geometric CV (%) and 95% CI for Proportions

Proportions (%), CV (%), geometric CV (%) and 95% CI for proportions will be rounded and displayed to the first decimal place.

8.5 Baseline

For the platelet count: Baseline will be the average of the assessment of Screening Visit and Day 1 Baseline Visit. The average is recorded in the database and will be used directly.

For other items: Baseline is defined as the last non-missing value taken at or before the study drug administration.

8.6 Visit Windows

No formal visit windowing will be conducted, except assign appropriate visit per study day for the records of the End of Study visit (VISIT 22). Only scheduled visit assessment will be used in

the by visit analyses. If multiple records are found within the visit window, the record closest to target date will be used for analysis purposes.

All assessments will be used when calculating cumulative and maximum duration of platelet response. The visit target date will be used to impute the missing visit date.

All assessments during scheduled and unscheduled visits will be listed in the data listing and presented in individual subject figures.

| Analysis Visit | Analysis Window Target | Analysis Window Beginning Timepoint | Analysis Window Ending Timepoint |
|--------------------|------------------------|-------------------------------------|----------------------------------|
| Baseline | 1 day | - | 1 day |
| Visit 3 (Day 5) | 5 days | 2 days | 6 days |
| Visit 4 (Day 8) | 8 days | 7 days | 11 days |
| Visit 5 (Week 2) | 14 days | 12 days | 17 days |
| Visit 6 (Week 3) | 21 days | 18 days | 24 days |
| Visit 7 (Week 4) | 28 days | 25 days | 35 days |
| Visit 8 (Week 6) | 42 days | 36 days | 49 days |
| Visit 9 (Week 8) | 56 days | 50 days | 63 days |
| Visit 10 (Week 10) | 70 days | 64 days | 77 days |
| Visit 11 (Week 12) | 84 days | 78 days | 91 days |
| Visit 12 (Week 14) | 98 days | 92 days | 105 days |
| Visit 13 (Week 16) | 112 days | 106 days | 119 days |
| Visit 14 (Week 18) | 126 days | 120 days | 129 days |
| Visit 15 (Week 19) | 133 days | 130 days | 136 days |
| Visit 16 (Week 20) | 140 days | 137 days | 143 days |
| Visit 17 (Week 21) | 147 days | 144 days | 150 days |
| Visit 18 (Week 22) | 154 days | 151 days | 157 days |
| Visit 19 (Week 23) | 161 days | 158 days | 164 days |
| Visit 20 (Week 24) | 168 days | 165 days | 171 days |
| Visit 21 (Week 25) | 175 days | 172 days | 178 days |
| Visit 22 (Week 26) | 182 days | 179 days | 299 days |

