### 5.3 Withdrawal Criteria

Participation of a subject in this clinical study may be discontinued for any of the following reasons:

- The subject withdraws consent or requests discontinuation from the study for any reason
- Occurrence of any medical condition or circumstance that exposes the subject to substantial risk and/or does not allow the subject to adhere to the requirements of the protocol
- Subject non-compliance or unwillingness to comply with the procedures required by the protocol
- Subject failed to meet inclusion/exclusion criterion

- Any SAE, clinically significant AE, severe laboratory abnormality, intercurrent illness, or other medical condition which indicates to the Investigator that continued participation is not in the best interest of the subject
- Pregnancy
- Investigator discretion
- Sponsor request
- Subject requires prohibited concomitant medication
- Termination of the study by the Sponsor or the regulatory authority

If a subject withdraws prematurely from the study due to the above criteria or any other reason, study staff should make every effort to complete the EOT assessments for the applicable phase. The reason for subject withdrawal must be documented in the eCRF.

In the case of subjects lost to follow-up, attempts to contact the subject must be made and documented.

If a subject is early terminated from the study, the EOT procedures should be performed. Subjects early terminated from the study will not be replaced, regardless of the reason for early termination.

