13.3.1 Laboratory Parameters and Change from Baseline by Visit

Population: Safety Set

Target Phases: Core Phase, Extension Phase

Visits:

- Core Phase: Baseline, Visit 4 (Day 8), Visit 10 (Week 10), Visit 13 (Week 16), Visit 22 (Week 26), Follow-up (Week 1), Follow-up (Week 2), Follow-up (Week 3), Follow-up (Week 4)
- Extension Phase: E 1 (Month 1), E 2 (Month 2), E 4 (Month 4), E 5 (Month 5), E 7 (Month 7), E 8 (Month 8), E 10 (Month 10), E 11 (Month 11), E 13 (Month 13), E 14 (Month 14), E 16 (Month 16), E 17 (Month 17), E 19 (Month 19), E 20 (Month 20), E 22 (Month 22), E 23 (Month 23), E 24 (Month 24)

Analysis items:

- For the parameters to be analyzed refer to Table 1 in [13.3 Laboratory data](#)

Contents:

- Summary statistics of actual value and change from baseline of laboratory tests for each visit are calculated.

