13.3.2 Laboratory Parameters with any Abnormal Measured Values by Visit

Population: Safety Set

Target Phases: Core Phase, Extension Phase

Visits:

- Core Phase: Baseline, Visit 4 (Day 8), Visit 10 (Week 10), Visit 13 (Week 16), Visit 22 (Week 26), Follow-up (Week 1), Follow-up (Week 2), Follow-up (Week 3), Follow-up (Week 4)
- Phase: E 1 (Month 1), E 2 (Month 2), E 4 (Month 4), E 5 (Month 5), E 7 (Month 7), E 8 (Month 8), E 10 (Month 10), E 11 (Month 11), E 13 (Month 13), E 14 (Month 14), E 16 (Month 16), E 17 (Month 17), E 19 (Month 19), E 20 (Month 20), E 22 (Month 22), E 23 (Month 23), E 24 (Month 24)

Analysis items:

- For the parameters to be analyzed refer to Table 1 in [13.3 Laboratory data](#)

Contents:

- The number and proportion of subjects with any abnormal measured values (High/Low) at each visit are calculated.

Definitions:

- The number of target population by each analysis visit is calculated.
- Abnormal measured values are defined as below:
 - High: actual value > upper limit of normal
 - Low: actual value < lower limit of normal
- The denominator to calculate proportion of subject with any abnormal measured values (High/Low) is the number of target population by each analysis visit (excluding discontinued subject before or at that visit).

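### In the Core Phase, the early-termination lab panel of a subject who stops before Day 179 is usually re-assigned to a visit that neither lab table lists

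*SAP*

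**What the plan says.** Protocol 5.3 states: "If a subject is early terminated from the study, the EOT procedures should be performed". Protocol 7.2.5 (Visit 22/Week 26, EOT) includes blood for central laboratory tests, and Appendix A marks chemistry, hematology and coagulation at that visit.

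SAP 8.6 applies no formal windowing "except assign appropriate visit per study day for the records of the End of Study visit (VISIT 22"). Its window table covers every visit from Visit 3 to Visit 22, for example "Visit 4 (Day 8) | 8 days | 7 days | 11 days". Visit 22 begins at Day 179. On which records count, it says "Only scheduled visit assessment will be used in" the by-visit analyses, and "If multiple records are found within the visit window, the record closest to" the target date is the one kept. It adds: "All assessments during scheduled and unscheduled visits will be listed in the data listing".

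SAP 13.3.1 gives the visits for the lab summary: "Core Phase: Baseline, Visit 4 (Day 8), Visit 10 (Week 10), Visit 13 (Week 16), Visit 22 (Week 26), Follow-up (Week 1"), continuing to Follow-up Week 4. SAP 13.3.2 uses the same Core Phase list and states: "The number and proportion of subjects with any abnormal measured values (High/Low) at each visit are calculated". Its denominator leaves out subjects who discontinued before or at the visit. Neither section has a row for early termination, last on-treatment value or worst post-baseline value, and the SAP has no lab shift table. Listing 16.2.8.1 covers laboratory parameters for the Core Phase Safety Set.

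**The concern.** Each rule is reasonable alone. Re-assigning an early EOT record by study day keeps a Week 6 sample out of the Week 26 summary. Limiting the lab tables to visits with scheduled labs keeps out empty rows. Together they leave a gap: the re-assignment can send an EOT panel to any of Visits 3 to 21, but the tables have a place for it at only three of them.

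The panel lost is the last safety sample from a subject who stopped, so the tables would lean towards subjects who stayed on treatment. Safety is a secondary objective of the Core Phase. Adverse event reporting covers only part of the gap. Protocol 9.1 asks for clinically significant abnormal findings to be reported as adverse events, but also says lab abnormalities are not adverse events unless they come with signs or symptoms or need medical intervention. An asymptomatic abnormality at termination could therefore be missing from both the adverse event tables and the lab tables.

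**Working it through.** The plan states no figure on this point, so there is none to reproduce. The check counts days in the SAP 8.6 window table. Stop day here means the study day of the EOT sample.

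**Inputs**
- SAP 8.6: Visit 3 starts at Day 2, Visit 21 ends at Day 178, and Visit 22 covers Days 179 to 299. The windows are contiguous, so each day from 2 to 178 belongs to exactly one visit before Visit 22.
- SAP 13.3.1 and 13.3.2: the on-treatment visits listed before Visit 22 are Visits 4, 10 and 13, which is 3 of the 19 visits from 3 to 21.

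**Step 1: days that map to a listed visit**
- Visit 4, Days 7 to 11: 11 − 7 + 1 = 5
- Visit 10, Days 64 to 77: 77 − 64 + 1 = 14
- Visit 13, Days 106 to 119: 119 − 106 + 1 = 14
- Total: 5 + 14 + 14 = 33

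**Step 2: days that map to an unlisted visit**
- Possible stop days: 178 − 2 + 1 = 177
- Unlisted: 177 − 33 = 144, and 144/177 = 81.4%

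**Step 3: sensitivity to the starting day**
- From Day 9: 170 days, of which 3 + 14 + 14 = 31 are listed; 139/170 = 81.8% unlisted
- From Day 29: 150 days, of which 28 are listed; 122/150 = 81.3% unlisted

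**Step 4: the closest-to-target rule.** If the scheduled lab was drawn on its target day (8, 70 or 112), an EOT panel later in the same window is dropped in its favour. This affects Days 9–11 (3), 71–77 (7) and 113–119 (7), 17 days in all. Then 33 − 17 = 16 days leave the EOT panel tabulated, and 177 − 16 = 161 do not: 161/177 = 91.0%.

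**Step 5: share of all post-baseline panels of an early stopper.** Assume even stop days, scheduled labs on target and no follow-up lab. Summed over the 177 stop days, the scheduled panels drawn before the stop number 170 (Day 8) + 108 (Day 70) + 66 (Day 112) = 344, or 344/177 = 1.94 per subject. Adding one EOT panel per stop day gives 344 + 177 = 521 panels.
- Untabulated: 144/521 = 27.6%
- With the closest-to-target rule: 161/521 = 30.9%

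**Step 6: the 13.3.2 denominator.** A panel that lands on Visit 4, 10 or 13 comes from a subject who stops in that window. Because the denominator leaves out subjects discontinued before or at the visit, that subject may be removed from it even though the result has a row.

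**The case against.** The strongest defence is that little is lost. Every value is in Listing 16.2.8.1, and with about 19 subjects in one arm a full listing can be read line by line. A lab abnormality serious enough to stop treatment would normally be reported as an adverse event and tabulated without reference to visit windows. These points stand and limit the consequence. They do not put the panel into the lab summaries, and the adverse event route misses asymptomatic findings.

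It can also be argued that an appropriate visit, for labs, means the nearest visit with a lab row. The SAP does not say so, and its single window table gives every visit its own range. At best the rule is ambiguous.

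Three stronger readings are tempting and are not supported:
- A reader might infer that most labs of early stoppers vanish. Their scheduled labs at Baseline and at Visits 4, 10 and 13 stay in the tables, as does a Visit 30 lab if taken. Only the EOT panel is affected.
- A reader might infer that excluding unscheduled visits hides many samples. The minimum assessments for an unscheduled visit (Protocol 7.2.8, Appendix A) include no central lab panel. Extra labs are optional, and keeping unscheduled values out of by-visit summaries is ordinary practice.
- A reader might extend the point to the Extension Phase. SAP 8.6 gives no Extension windows and re-assigns only Visit 22.

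**Conclusion.** The point holds for one panel per early stopper in the Core Phase. Under the stated rules, 144 of 177 possible stop days send the EOT panel to a visit that neither lab table lists. This is about 81% with evenly spread stop days, and about 91% if scheduled labs were drawn on target and the closest-to-target rule also applies. Under the same even spread, 28% to 31% of an early stopper's post-baseline panels go untabulated.

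The day counts follow directly from the SAP. The percentages rest on evenly spread stop days, because the documents give neither a dropout rate nor its timing, so the number of affected subjects is unknown and could be none. A lost value also cannot be expressed as a share of the planned enrolment, because 13.3.2 uses a by-visit denominator.

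No data are lost, and the primary endpoint and its hurdle are untouched. This is an inexpensive improvement to the safety tables.

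**What to change.** 1. In SAP 13.3.1 and 13.3.2, add a last on-treatment / early-termination row that takes the EOT sample whatever its study day. In 13.3.2, state that the exclusion of discontinued subjects does not apply to this row; otherwise it would remove the subjects the row is meant to show.
2. In SAP 13.3.2, add a worst post-baseline, any-time High/Low row that uses all post-baseline central results: scheduled, EOT and any unscheduled. Its denominator should be the Core Phase Safety Set subjects with at least one post-baseline result.
3. Keep the Visit 22 re-assignment in SAP 8.6. Exempting lab records would label a sample from, say, Day 30 as Week 26 and mix early stoppers into that summary.

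The cost is a few lines of SAP text and the programming of two additional row types. No new data are needed, and the existing by-visit rows do not change.

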8.7 Handling of Missing Data

8.7.1 Handling of Partial Dates for Adverse Events

When determining treatment-emergent adverse events (TEAEs), partial dates with missing day will be handled as follows:

- If AE onset day is missing, AE onset day will be set to the first day of the month unless it is the same month and year as first dose date. In this case, the start date will be assumed to be the first date of treatment.

*AE onset month and AE onset year won't be missing.

** Causality and Severity won't be missing.

9 Subject Disposition

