#### 7.1 Pre-enrollment Phase

# 7.1.1 Visit 1/Day -28 to Day -1: Screening

The following assessments must be completed at the Screening Visit:

- Collect signed and dated informed consent prior to any study procedures.
- Review of inclusion/exclusion criteria (Section 5).
- Record demographic information.
- Perform physical exam
- Complete medical/medication/surgical history to include all past significant illnesses and/or surgeries (in the opinion of the Investigator) and all medications currently being taken (including non-prescription medications, vitamins, dietary supplements, and herbal products).
- Collect ITP history
  - o Date of diagnosis.
  - Number of platelet transfusions in the previous 1 year, including date of last platelet transfusion.
  - o Number of previous hospitalizations for ITP.
  - o Number of previous significant bleeding events (e.g., blood loss ≥100 mL).
  - o Other previous treatments for ITP, including duration.
- Collect height and weight to determine body mass index (calculated by eCRF).
- Collect vital signs (blood pressure and pulse). Vital signs should be taken after sitting for 5 minutes whenever possible. Vital signs should be taken prior to any blood draws.
- Collect blood for central laboratory tests (see Section 9.7).
- Collect platelet counts via local lab.
- Perform pregnancy test for female subjects of childbearing potential.
- Review and record AEs that may have occurred after signing informed consent.
- Record concomitant medications and procedures.

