#### 9 SAFETY ASSESSMENTS

## 9.1 Adverse Events

An adverse event is defined as any untoward medical occurrence in a subject administered a pharmaceutical product, which does not necessarily have a causal relationship with this treatment. An AE can therefore be any unfavorable and/or unintended sign (including an abnormal laboratory finding), symptom, or disease temporally associated with the use of an investigational medicinal product, whether or not related to the investigational medicinal product. All AEs, including observed or volunteered problems, complaints, or symptoms, are to be recorded on the appropriate eCRF.

Adverse Events, which include clinical laboratory test variables, will be monitored, and documented from the time of informed consent until the time the subject is discharged from the study. Subjects should be instructed to report any AE that they experience to the Investigator. Beginning with the Informed Consent signature, Investigators should make an assessment for AEs at each visit and record the event on the appropriate AE eCRF. Events associated with disease progression should not be reported as AEs/SAEs. However, if in the Investigator's opinion the disease progression is manifesting in an unusual or uncharacteristic manner, the associated events should be reported as AEs/SAEs, as appropriate.

Wherever possible, a specific disease or syndrome (i.e., diagnosis) rather than individual associated signs and symptoms should be identified by the Investigator and recorded on the eCRF. However, if an observed or reported sign or symptom is not considered a component of a specific disease or syndrome by the Investigator, it should be recorded as a separate AE on the eCRF. Additionally, the condition that led to a medical or surgical procedure (e.g., surgery, endoscopy, tooth extraction, or transfusion) should be recorded as an AE, not the procedure.

Any medical condition already present at the Screening Visit should not be reported as an AE unless the medical condition or signs or symptoms present at baseline changes in severity, frequency, or seriousness at any time during the study. In this case, it should be reported as an AE.

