13.2 Adverse Events

| Term | Definition |
|---|--|
| Adverse Event (AE) | An adverse event is defined as any untoward medical occurrence in a subject administered a pharmaceutical product, which does not necessarily have a causal relationship with this treatment. An AE can therefore be any unfavorable and/or unintended sign (including an abnormal laboratory finding), symptom, or disease temporally associated with the use of an investigational medicinal product, whether or not related to the investigational medicinal product. |
| Treatment-emergent Adverse Event (TEAE) | A treatment-emergent adverse event is an event that emerges during treatment having been absent pre-treatment, or worsens relative to the pre-treatment state. |
| Causality Assessment | The relationship of an AE to the administration of the study drug is to be assessed according to the following definitions: 
 - No (unrelated, not related, no relation) – The time course between the administration of study drug and the occurrence or worsening of the AE rules out a causal relationship and another cause (concomitant drugs, therapies, complications, etc.) is suspected. - Yes (related) – The time course between the administration of study drug and the occurrence or worsening of the AE is consistent with a causal relationship and no other cause (concomitant drugs, therapies, complications, etc.) can be identified. |
| Related TEAE | A related treatment-emergent adverse event is a treatment-emergent adverse event whose Investigator causality assessment is related. |

| | |
|---|---|
| Serious TEAE/ Serious Related TEAE | 
A serious TEAE is a treatment-emergent adverse event which is considered serious if, in the view of either the Investigator or Sponsor, it results in any of the following outcomes:
 
 - Death - A life-threatening adverse event - Requires hospitalization or prolongation of existing hospitalization - A persistent or significant disability/incapacity or substantial disruption of the ability to conduct normal life functions - A congenital anomaly/birth defect - An important medical event 
A serious related TEAE is a serious TEAE whose Investigator causality assessment is related.
 |

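### SAP 8.7.1 ignores the stop date, so an AE with a missing onset day in the first-dose month counts as treatment-emergent even when it is known to have ended before first dose

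*SAP*

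**What the plan says.** SAP 8.7.1 is the SAP's only rule for incomplete AE dates, and it opens with its purpose: "When determining treatment-emergent adverse events (TEAEs), partial dates with missing day will be handled as follows". A missing onset day is set to the first of the month "unless it is the same month and year as first dose date"; for that exception, "In this case, the start date will be assumed to be the first date of treatment". A footnote adds that "AE onset month and AE onset year won't be missing", so the day is the only part of the onset date that needs imputing.

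SAP 13.2 defines a TEAE as "an event that emerges during treatment having been absent pre-treatment", or one that worsens relative to the pre-treatment state. The same section restricts the AE tables to TEAEs and sends all other events to the listings.

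AE collection starts before dosing. Protocol 9.1 has AEs "documented from the time of informed consent until the time the subject is discharged from the study". The screening visit, "Visit 1/Day -28 to Day -1: Screening" (Protocol 7.1.1), includes the step "Review and record AEs that may have occurred after signing informed consent", and Protocol 7.2.1 repeats the review at Baseline.

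**The concern.** First-dose imputation is a sensible default when nobody can tell whether an event began before or after dosing. Once the stop date is known to precede the first dose, that uncertainty is gone: the event began and ended before treatment. SAP 8.7.1 still dates its onset to the first dose, because matching month and year is its only condition. The record then has an onset later than its end, and a pre-treatment event enters the TEAE tables. Those tables are small and have no control arm in which such errors could balance out.

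The SAP already applies the missing logic elsewhere. In SAP 10.3, a medication that stops before the first Core Phase dose is classified as prior. Neither 8.7.1 nor the TEAE definition makes the corresponding check for AEs.

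**Working it through.** The plan gives no figure on this point, so the check is to apply the rule as written.

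**Inputs**
- Imputed onset: the first-dose date if month and year match, otherwise the first of the month (SAP 8.7.1).
- TEAE status: taken here as imputed onset on or after first dose, the natural reading of 8.7.1 and 13.2.
- Time to onset: (onset date − treatment start date + 1) / 30.4375 months (SAP 13.2.8).
- Planned size: about 19 (Protocol 4.1); at least 19 (SAP 4.2).

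**Worked cases, first dose 20 June, onset day missing**

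| Onset month | Stop date | Onset under 8.7.1 | TEAE under 8.7.1 | Onset after stop? | TEAE with a stop-date check |
|---|---|---|---|---|---|
| June | 12 June | 20 June | Yes | Yes, by 20 − 12 = 8 days | No |
| May | 12 June | 1 May | No | No | No |
| June | ongoing | 20 June | Yes | No | Yes |
| June | 25 June | 20 June | Yes | No | Yes |

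Only the first row is wrong, and it is wrong for any dates of that kind. Let D be the first-dose date and S the stop date. The rule sets onset to D. If S < D, onset is after the stop date, and because onset equals D the event counts as a TEAE.

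**Conditions needed together:** (a) the onset day is missing; (b) onset is in the same month and year as first dose; (c) the recorded stop date is before first dose.

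**How much of screening meets condition (b).** Assume a full 28-day screening period and first doses spread evenly over a 365-day year. For a first dose on day d of a month, min(d − 1, 28) of the preceding 28 days fall in that month. Summed over d, this gives 462 for a 31-day month, 434 for a 30-day month and 378 for a 28-day month. Then (7 × 462 + 4 × 434 + 378) / (365 × 28) = 5,348 / 10,220 = 0.523. About 52% of screening days share a month with the first dose. This shows that the case can arise. It does not show how often, because (a) and (c) must also hold.

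**Size per affected subject**
- Incidence of the term: 1/19 = 5.3 percentage points, and less if the Safety Set is larger than 19. An overall TEAE row moves only if this is the subject's sole TEAE.
- Time to onset: (0 + 1) / 30.4375 = 0.03 months, so the event appears in the under-3-months category as if it began on the first day of treatment.

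**The case against.** The strongest reply is that the case is rare and the TEAE definition already excludes it. Conditions present at the Screening Visit are not AEs unless they change (Protocol 9.1). AEs are reviewed at both Screening and Baseline. Missing data are queried with the site (Protocol 11.1.5), and an eCRF is complete only once missing and inconsistent data are accounted for (Protocol 11.1.1). A short screening event with a known stop date but still no onset day should be uncommon. Safety is descriptive and single-arm, the error over-counts events rather than hiding them, and the AE listing (16.2.7) might reveal an impossible pair of dates.

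The points on rarity and low consequence stand. The appeal to the definition does not settle the matter. SAP 8.7.1 is the stated rule for determining TEAEs and carries no override, so the two sections give opposite answers for the same record and the programmer must choose.

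Two stronger readings are tempting, and the documents support neither. A reader might infer that every screening event that resolved before dosing is miscounted; the worked cases show that this needs all three conditions. A reader might also infer that the first-of-month branch moves Extension events into the Core Phase tables. But 8.7.1 covers only TEAE determination, and no section assigns an AE to a phase by its imputed date. The combined Core and Extension incidence would not change in any case. With the day unknown, the event may in fact belong to the Core Phase.

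**Conclusion.** The rule gives a wrong result as written, in one narrow case: onset day missing, onset in the first-dose month and year, and a recorded stop date before first dose. Such an event gets an onset after its own end and is tabulated as a TEAE, contrary to SAP 13.2. The effect is at most about 5.3 percentage points per affected subject on a term's incidence in the overall tables, given a Safety Set of at least 19. The number of affected subjects cannot be derived from the documents and is likely small. The primary endpoint does not depend on this rule. The conclusion assumes that an AE stop date is collected; the documents do not describe the AE form fields. This is a minor correction.

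**What to change.** Add to the first-dose branch of SAP 8.7.1: *unless the AE stop date is known to be before the first-dose date, in which case the event is classified as pre-treatment and not treatment-emergent.* Keep first-dose imputation when the stop date is missing, or is on or after first dose, so the conservative default survives wherever timing is uncertain.

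The cost is one clause in the SAP and one extra condition in the TEAE derivation. No new data are needed if the stop date is already collected, which should be confirmed against the AE form. SAP section 2 has the SAP locked before the Core Phase database lock, so the change belongs before that point.
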